In each 35-minute test sequence, vital signs will be continuously monitored with pupillary measurements taken every 2.5 minutes. During the first 10 minutes of the 35-minute sequence, remiferitanil will be infused at a predetermined rate described below. Sedation assessment will be made using the Pasero Opioid-Induced Sedation (POSS) Scale.²⁹

Opioid Infusion:

The remifentanil will be infused for 10 minutes- at a rate of 0.2µg/kg/minute for the first 5 minutes, followed by 0.3µg/kg/minute for the next 5 minutes. After remifentanil discontinuation, pupillary measurements will continue every 2.5 minutes for the remaining 25-minute recovery phase. To avoid the costs and stimulating effect of sequential blood drawing, or the added discomfort of arterial line placement to facilitate repeated blood sampling, we do not plan to measure remifentanil blood concentration, choosing instead to use an infusion protocol based on the Minto model that, when given to eligible subjects, should achieve an estimated maximum effect site concentration of 4-6 ng/mL, a level known to produce near-maximum isoflurane MAC reduction and high probability of apnea.²⁹⁻³¹

Outcomes:

Primary outcome is the correlation between PUAL and intensity of opioid exposure (represented by time-points corresponding to progressively increasing and declining estimated opioid concentrations) and the ability to discriminate zero-moderate versus high-toxic opioid effect. The discrimination of PUAL to identify high-risk opioid exposure will be determined by construction of receiver operator characteristic (ROC) curves.

Subjects:

Eligible subjects will be 40-60 years of age, recruited from flyers posted around the UCSF campus, and from an advertisement placed on Craigslist. Exclusion criteria will include use of opioid agonist or antagonist within the prior thirty days, any cardiopulmonary or neurologic condition, baseline SpO2 < 95%, diabetes, obstructive sleep apnea (OSA), BMI > 35 kg/m2, current or previous substance use disorder, ocular disease (including glaucoma), prior ocular surgery, use of any prescription ocular medication, use of medications known to affect pupillary characteristics (see below), blindness, previous episodes of serotonin syndrome, or inability to provide written informed consent.

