Use of any alpha-adrenergic blocking medication for urinary symptoms or anticholinergic medications

History or ocular surgery (ie, cataract surgery, vitrectomy), ocular disease (ie, glaucoma), or use of topical eye medications

Use of mood stabilizers or antidepressant medications (including serotonin-reuptake inhibitors or MAO-inhibitors) within past 30 days

Use of stimulant medications (amphetamines, including medications used for appetite suppression or attention deficit disorder)

Use of phosphodiesterase inhibitor medications (usually given for erectile dysfunction) within the past 7 days

Inability to read or understand English

Any condition prohibiting delivery of oxygen by nasal cannula

Anxiety or panic disorders

Severe motion sickness or intractable vomiting after prior anesthesia

Fever, upper respiratory infection, or illness of any variety within 8 weeks of participation

Exclusion criteria involving opioid use or substance use disorder will be determined by self-report from the potential subject.

DATA COLLECTION

Subject data including subject number, initials, age, sex, race, height and weight, along with time-stamped drug administration and vital signs, will be collected on a source document anesthetic record, which will be scanned and stored on a HIPAA-compliant secure location. Pupillary measures will be collected on a Neuroptics PLR-3000 device, and the date and times of the scans will be correlated to the times of each subject's data. The pupillary scans will be downloaded by Bluetooth to a csv file that will be stored on an encrypted laptop computer.

DATA ANALYSIS

We plan to test 20 subjects aged 40-60 under paired conditions- absent versus uninterrupted conversational interaction- over a 35-minute period. Interim analysis is planned after 10 subjects are studied.

Correlation between PUAL and opioid concentration:

We will examine PUAL and estimated opioid effect site concentration during both drug infusion (0-10 minutes, where opioid concentrations progressively increased) and recovery (10-35 minutes, where opioid concentrations progressively decline). Each 2.5-minute point will be treated as an ordinal variable "time", and opioid effect-site concentrations will be calculated at each time point according to the Minto pharmacokinetic model estimates.²⁹ The effect of time (as surrogate for opioid concentration) on PUAL will be assessed using a linear mixed effects model.

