Distinguishing between zero-low risk versus high-risk, toxic opioid conditions by PUAL: We will collect PUAL data at times when estimated opioid effect site concentrations in all subjects are consistently low (< 2.0 ng/mL) versus high (>2.4 ng/mL). A receiver operating characteristic analysis using dichotomized PUAL values will be constructed to determine PUAL's ability to distinguish between low-risk versus high-risk opioid exposure in the 40-60year-old subjects. This ROC curve will be compared to that of subjects in the 20-39 year-old range, and interval likelihood ratios that identify high, indeterminant and low risk will be reported.

SAMPLE SIZE CALCULATION

The primary objective of this study is to assess PUAL's ability to identify high-risk opioid effect in older adults. In the previous study in younger adults, we used a remifentanil infusion that consistently produced zero to moderate opioid effect at 2 time points (baseline and 2.5 minutes) and high opioid effect at 4 time points (5.0, 7.5, 10.0, and 12.5 minutes). We assessed the ability of PUAL to discriminate using the area under the ROC curve (AUROC).

In that study the AUROC was slightly *lower* under quiet vs. interactive conditions (0.95 vs 0.97), and the standard error of the summary AUROC was 0.01. If the discrimination is substantially lower in older adults, we would expect an AUROC of 0.875. A sample size of 20 participants would produce a 95% confidence interval of width 0.12 (0.81 to 0.93) and a standard error of 0.0275.³⁷ The standard error of the difference in AUROCs would be 0.03 and would provide 80% power to detect a difference in AUROCs of 7.5% at the 0.05 significance level.³⁸

In addition, we intend to evaluate the same PUAL intervals as found in our previous analysis of 20-39-year-old subjects:

- PUAL 0.00 to <0.04 = high-risk opioid effect, interval likelihood ratio = 14.59;
- PUAL \geq 0.04 to 0.13 = indeterminate effect, interval likelihood ratio = 1.12;
- PUAL \ge 0.14 = zero or low risk opioid effect, interval likelihood ratio = 0.02.

We will calculate interval likelihood ratios in the 40-60-year-olds.³⁹ For high opioid effect, we expect an interval likelihood ratio of approximately 10. Our sample size of 20 should allow estimation with a 95% confidence interval 3.3 to 30.

References:

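### The ROC rule for the 40-60-year-olds, as worded, admits late recovery readings to the low class, while the younger benchmark is described on six time points from 0 to 12.5 minutes

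*Combined protocol and SAP*

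**What the plan says.** Under Sample Size Calculation, the low side of the previous study's infusion is given as "zero to moderate opioid effect at 2 time points (baseline and 2.5 minutes"). The text then turns to the high side, which it gives as "high opioid effect at 4 time points (5.0, 7.5, 10.0, and 12.5 minutes"). The next sentence says that discrimination was assessed by AUROC. The precision and power for the new study follow from there.

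Under Data Analysis, the rule for the new cohort is worded differently: "We will collect PUAL data at times when estimated opioid effect site concentrations in all subjects are consistently low (< 2.0 ng/mL) versus high (>2.4", both cut-offs being in ng/mL. It names no time points and does not mention recovery. The same paragraph then says "This ROC curve will be compared to that of subjects in the 20-39 year-old range".

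Under Opioid Infusion, after the drug is stopped "pupillary measurements will continue every 2.5 minutes for the remaining 25-minute recovery phase". Data Analysis defines the second phase as "recovery (10-35 minutes, where opioid concentrations progressively decline") and has a concentration calculated at every time point.

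Preliminary Data leaves open whether the younger data come from the quiet sequence alone or from both sequences. No section says that the younger ROC will be rebuilt under the concentration rule.

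**The concern.** AUROC is the probability that a randomly chosen high-exposure reading shows a lower PUAL than a randomly chosen low-exposure reading. It does not depend on the ratio of high to low readings, but it does depend on which readings form the low class. PUAL at a given low concentration late in recovery need not equal PUAL at baseline or 2.5 minutes.

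If the older ROC has a low class that includes recovery readings and the younger one does not, a difference between the curves could reflect the choice of readings as well as age. The effect of age is the question the Aims pose. The interval likelihood ratios have the same problem, because they share the low class as denominator. The choice of readings could also be settled after the data are seen, since the text does not fix it.

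**Working it through.** **1. Readings scheduled and listed.** One reading every 2.5 minutes from 0 to 35 minutes gives 35/2.5 + 1 = 15 time points. Six are listed for the younger cohort: 0, 2.5, 5, 7.5, 10 and 12.5 minutes. The other nine run from 15 to 35 minutes. By the plan's own phase definition 12.5 minutes is already a recovery reading, on the high side. What the six-point set lacks is low-concentration recovery readings.

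**2. Do late recovery readings meet the low rule?** The plan expects a maximum effect-site concentration of 4-6 ng/mL. Take 6 ng/mL at 10 minutes and, as a simplification, single-exponential decline. To be still at 2.0 ng/mL at 35 minutes would need a half-life of 25/log2(6/2) = 25/1.585 = 15.8 minutes. Any faster decline puts at least the last reading in the low class, and Preliminary Data calls the drug ultra-short acting. The number k of qualifying recovery time points is not given. If the half-life is assumed to be 2-7 minutes, a start at 4-6 ng/mL gives k = 6 to 9, keeping 12.5 minutes as high. Below, k is treated as unknown from 1 to 9.

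**3. The plan's own precision figures.** The plan cites the Hanley-McNeil formula. With A = 0.875, n1 high and n0 low readings, all treated as independent:

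SE² = [A(1−A) + (n1−1)(Q1−A²) + (n0−1)(Q2−A²)]/(n1·n0), where Q1 = A/(2−A) = 0.7778 and Q2 = 2A²/(1+A) = 0.8167.

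Six-point set: n1 = 20 × 4 = 80 and n0 = 20 × 2 = 40.

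SE² = (0.1094 + 79 × 0.01215 + 39 × 0.05104)/3200 = 3.060/3200, so SE = 0.0309. The 95% CI is 0.814 to 0.936, width 0.121.

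| Low time points | Low readings | SE | CI width |
|---|---|---|---|
| 2 (six-point set) | 40 | 0.0309 | 0.121 |
| 2 + 1 | 60 | 0.0292 | 0.114 |
| 2 + 6 | 160 | 0.0268 | 0.105 |
| 2 + 9 | 220 | 0.0264 | 0.103 |

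The stated width of 0.12 fits 80/40. The stated SE of 0.0275 does not; it would need about 100 to 120 low readings against 80 high. The stated figures also disagree with each other: 0.875 ± 1.96 × 0.0275 is 0.821 to 0.929, width 0.108.

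**4. Likelihood-ratio interval (stated as 10, 3.3 to 30).** SE of ln LR = √[(1−p1)/(p1·n1) + (1−p0)/(p0·n0)]. Assume p1 = 0.75 of high readings fall in the interval, so p0 = 0.075.

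- 80/40: √(0.00417 + 0.30833) = 0.559, giving 3.34 to 29.9.
- 80/180: 5.9 to 17.0.

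Varying p1 from 0.6 to 0.9, 80/40 gives 2.9-34.5 to 3.7-26.9, and 80/180 gives 5.5-18.3 to 6.3-16.0. The stated interval fits 40 low readings.

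**5. How the low class enters the AUROC.** With equal numbers of readings per time point, the pooled AUROC is (2·A_early + k·A_rec)/(2 + k). The shift from the six-point value is therefore k/(k+2) × (A_rec − A_early). The weight k/(k+2) is 0.33, 0.60 and 0.80 for k = 1, 3 and 8. For illustration only, take A_early = 0.95 (the quiet-condition value) and an assumed A_rec of 0.85 to 0.98:

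- k = 3: 0.890 to 0.968
- k = 8: 0.870 to 0.974

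If A_rec is also 0.95, the shift is zero. The documents give no A_rec.

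**The case against.** The strongest reply is that only one selection rule is stated for this study. The six time points describe the earlier study, and the repeated stress on consistency, with a similar infusion, lets the rule be read as meaning the same six points. That reading is possible. However, "We will collect PUAL data at times when estimated opioid effect site concentrations in all subjects are consistently low" carries no limit to it, and the primary outcome covers both rising and declining concentrations. Someone following the text literally would include late recovery.

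It can also be said that working from the younger cohort's data leaves a common rule open. That is true, but no section commits to one.

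A reader might infer that the sample size demonstrably rests on 80 and 40 readings. The text gives no counts. Two stated figures support the inference and the stated SE does not. A reader might also infer a known bias, close to the planned difference of 0.075, from the illustration above. That is not supported: every shift there comes from an assumed recovery AUROC, and the documents report neither lag nor overshoot of PUAL, only that it rose during recovery. Nor is precision harmed, since the formula SE falls as low readings are added.

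A fair objection to relying on the six-point set alone is that every low reading then precedes every high reading, so exposure is confounded with elapsed time. This stands and shapes the fix.

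**Conclusion.** The point holds as a conflict between the described benchmark set and the wording of the new cohort's ROC rule, and it bears on the main between-cohort comparison. That late readings qualify as low rests on the plan's 4-6 ng/mL maximum and on an effective half-life shorter than about 16 minutes after the infusion stops, under the single-exponential simplification. How many qualify needs the pharmacokinetic model. Recovery could supply anything from a third of the low class (k = 1) to about four-fifths (k = 9, 9/11 = 0.82).

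The documents do not prove that unlike sets will be compared, and neither the direction nor the size of a shift in AUROC can be derived from them. It should be settled before the cohorts are compared.

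**What to change.** In the ROC paragraph of Data Analysis:

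- List the time points that enter the ROC and say whether recovery readings after 12.5 minutes count.
- Apply the identical rule to both cohorts, and recompute the younger cohort's AUROC and interval likelihood ratios under it before comparing.
- Base the older-versus-younger comparison on the six-point set (0 to 12.5 minutes), because it matches the benchmark as described and the sizing as far as that can be inferred.
- Report alongside it an ROC that includes low-concentration recovery readings, computed the same way in both cohorts. This covers declining concentrations and offsets the time ordering of the six-point set.

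The cost is plan wording and one re-run on younger-cohort data that the plan already intends to use. No extra measurements are needed. The downside is that recovery readings leave the headline age comparison, which is why the second ROC should be shown with it.

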Opioid-induced respiratory depression (OIRD) confers significant safety risk, but its onset can be challenging to recognize. Hypoxia and related sequelae from OIRD may present abruptly, giving the clinician insufficient time to intervene and rescue before harm reaches the patient. Previous data showed that among healthy 20-39-year-old volunteers, incremental decline and eventual obliteration of pupillary unrest in ambient light (PUAL) occurred in a consistent manner during escalating opioid concentration from remifentanil infusion. Low and often obliterated PUAL were consistent markers of high-risk remifentanil exposure and coincident episodes of hypoxic respiratory depression, even while subjects remained alert. In this young adult age group, specific PUAL values discriminated between zero or low versus high-risk intensive opioid exposure with outstanding discrimination (AUROC = 0.9671 [0.9384 – 0.9958]).¹ We anticipate PUAL will develop into a useful tool in the future to guide clinical decision-making in patients receiving opioids on matters including choice of appropriate level of monitoring, consideration of supplemental oxygen, possible opioid de-escalation, and timely pursuit of non-opioid analgesic alternatives and support when necessary. To explore the generalizability of these findings, we plan to perform a similar study among subjects in an older age range (40-60 years). Although we anticipate that the PUAL decline and opioid intensity relationship will probably be similar across age ranges, the predictive value of specific PUAL thresholds may differ in older individuals due to age-related changes in normal pupil measurements and characteristics. Recent unpublished data from ambulatory subjects showed a modest decline in resting PUAL in subjects aged 50 and older compared to younger adult subjects. The physiologic vulnerability of older patients elevates the importance of early, reliable OIRD detection. Aging is accompanied by alteration of a variety of vital protective mechanisms, including blunting of chemoreceptormediated ventilatory responses to hypoxia and hypercapnia.^{2,3} Among subjects with sleep disordered breathing, older age is associated with more severe, prolonged desaturation episodes during upper airway obstruction.³

AIMS

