Subsequently we studied 20 healthy volunteers aged 20-39 years, to determine whether progressive decline of PUAL to zero or a lower limiting value would occur consistently as opioid exposure increased to the point of respiratory depression.¹ Participants received an intravenous infusion of remifentanil, an ultra-short acting opioid medication. As the dose and effect site concentrations incrementally rose, serial pupillary measures were taken every 2.5 minutes, including at times coinciding which clinically significant respiratory depression. We sought to determine whether PUAL declines consistently to zero or near zero in all subjects as opioid concentration builds to the point of respiratory depression. We found that in this group of participants aged 20-39, PUAL declined significantly over the course of the remifentanil infusion and rose significantly during recovery (p < 0.0001). Nearly all subjects reached 90% or greater PUAL suppression. PUAL showed outstanding discrimination in

distinguishing higher versus absent-moderate opioid exposure (AUROC = 0.957 [0.929 to 0.985] in all runs). For exploratory purposes this study had two infusion sequences, one conducted under normal "quiet" conditions, and the other during stimulating "interactive" conditions to estimate what if any role environmental stimulation may play in delaying or mitigating OIRD. Findings in younger subjects used for subsequent comparison to the older group will use the data from the control ("quiet") arm, or from both infusion sequences as appropriate.

In a separate study, to estimate normative ranges of PUAL in the general population across age groups, we evaluated 150 de-identified ambulatory subjects, collecting information only on age-range, (18-29, 30-49, 50-69, and \geq 70 years), diabetes, and use of opioid or beta-blocker medication in the previous 24-hour period. In that cohort we found a modest but statistically significant impact of age on PUAL, where subjects \geq 50 years of age had lower median PUAL values versus subjects under 50 years of age.

EXPERIMENTAL DESIGN AND METHODOLOGY OF PROPOSED STUDY

Design:

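### The younger-cohort AUROC standard error is printed as 0.01, but the protocol's own all-runs interval implies 0.0143; carried unrounded, the stated 7.5% difference does not reach 80% power

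*Combined protocol and SAP*

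**What the plan says.** All of this is in the combined protocol and SAP.

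- **Sample Size Calculation, younger cohort.** AUROCs are given by condition, "under quiet vs. interactive conditions (0.95 vs 0.97"), and "the standard error of the summary AUROC was 0.01".
- **Sample Size Calculation, older cohort.** If discrimination is substantially lower, "we would expect an AUROC of 0.875". Twenty participants are said to give a "95% confidence interval of width 0.12 (0.81 to 0.93) and a standard error of 0.0275".
- **Sample Size Calculation, comparison.** "The standard error of the difference in AUROCs would be 0.03", giving "80% power to detect a difference in AUROCs of 7.5% at the 0.05 significance level". Whether the test is one-sided or two-sided is not stated.
- **Preliminary Data.** The younger cohort's pooled result is "AUROC = 0.957 [0.929 to 0.985] in all runs". The section leaves open whether the comparator will be the quiet arm alone or both infusion sequences.
- **Opening summary.** A second younger-cohort figure appears, "AUROC = 0.9671 [0.9384 – 0.9958"].

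**The concern.** The comparison of AUROCs between age groups is the only one for which the plan states power, and its variance has two inputs: the older-cohort and younger-cohort standard errors. The older one is given to four decimals. The younger one is given to two, and the all-runs interval in Preliminary Data implies a value over 40% larger. Because the standard error is squared, the younger cohort's variance contribution is 0.000204 rather than 0.000100.

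The study is meant to show whether the PUAL scale needs modification in older adults. If the power is overstated, a finding of no difference between age groups would look more reassuring than it should.

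**Working it through.** **Method.** Normal approximation for two independent AUROCs: SE of the difference = √(SE_old² + SE_young²). Power = Φ(d/SE − z), with z = 1.645 one-sided or 1.960 two-sided. Difference detectable with 80% power = (z + 0.842) × SE. Standard error implied by a 95% interval = width/3.92.

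**1. The plan's own figures.** √(0.0275² + 0.01²) = √0.000856 = 0.0293, which prints as the stated 0.03. The stated difference is 0.95 − 0.875 = 0.075.

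- Printed 0.03, one-sided: Φ(2.500 − 1.645) = 80.4%; detectable difference 2.487 × 0.03 = 0.0746. This reproduces the plan's 80% and 7.5%.
- Printed 0.03, two-sided: Φ(2.500 − 1.960) = 70.5%.
- Unrounded 0.0293: 82.1% one-sided, 72.7% two-sided.

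**2. The standard error implied by the reported intervals.** All runs: (0.985 − 0.929)/3.92 = 0.056/3.92 = 0.0143. Opening summary: (0.9958 − 0.9384)/3.92 = 0.0146. A standard error of exactly 0.01 would give an interval of width 0.039, not 0.056. The all-runs figure is the better match for a summary AUROC, so 0.0143 is used below.

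**3. Carrying 0.0143 unrounded.** √(0.000756 + 0.000204) = 0.0310, which also prints as 0.03.

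| Difference 0.075, older SE 0.0275 | SE of difference | One-sided power | Two-sided power |
|---|---|---|---|
| Younger SE 0.01 | 0.0293 | 82.1% | 72.7% |
| Difference SE as printed | 0.03 | 80.4% | 70.5% |
| Younger SE 0.0143 | 0.0310 | 78.1% | 67.7% |

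With 0.0310 the difference detectable with 80% power is 2.802 × 0.0310 = 0.087 two-sided, or 2.487 × 0.0310 = 0.077 one-sided. For 80% one-sided power at 0.075, the younger standard error could be at most √((0.075/2.487)² − 0.0275²) = 0.0124, which is below 0.0143.

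If 7.5% were meant relative to 0.95, the difference would be 0.07125, and power with 0.0310 would be lower still: 74% one-sided, 63% two-sided.

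**4. The older-cohort input.** 0.875 ± 1.96 × 0.0275 is 0.821 to 0.929, of width 0.108. The printed interval, of width 0.12, implies 0.12/3.92 = 0.0306. With 0.0306 and 0.0143, SE of the difference = √(0.000936 + 0.000204) = 0.0338. Power for 0.075 is then about 72% one-sided and 60% two-sided, with detectable differences of 0.084 and 0.095.

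**5. If the quiet arm is the comparator.** Its standard error is not given. As an assumption, the Hanley-McNeil formula at 0.95 with 80 high and 40 low readings (20 subjects at four and two time points), treated as independent, gives 0.0188. With 0.0275, SE of the difference = √(0.000756 + 0.000353) = 0.0333, and power for 0.075 is about 73% one-sided and 61% two-sided.

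**The case against.** The strongest reply is rounding. To two decimals, 0.0143 is 0.01; the neighbouring AUROCs are also given to two decimals; and the SE of the difference prints as 0.03 with either input. A reader might infer that the plan literally used 0.01 in place of 0.0143. The documents do not show that. Indeed, a difference SE of exactly 0.03 back-solves to a younger value of √(0.03² − 0.0275²) = 0.012. This part of the reply stands. Rounding explains the printed digits, however, not the power: the one-sided 80.4% depends on using 0.03 rather than 0.0310.

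A reader might also take the loss to be larger. A two-sided test of 0.957 against 0.875, a difference of 0.082, gives 80.0% with 0.01 and 75.4% with 0.0143. The Sample Size Calculation never states that difference; its 7.5% is 0.95 − 0.875. For the stated difference, the one-sided change is from 80.4% to 78.1%, about two points, which some would call a reproduction of 80%.

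Nor should the whole fall to 68% two-sided be laid on this input. With 0.01, two-sided power is already 72.7%, so sidedness accounts for about 7 of the 12 points and the standard error for about 5.

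Finally, 0.0143 belongs to both sequences pooled, whereas 7.5% matches the quiet-arm AUROC, so 0.0143 is not necessarily the right replacement. That stands, and the fix allows for it.

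**Conclusion.** The point holds as a minor correction. The all-runs interval implies a younger-cohort standard error of 0.0143 where the plan prints 0.01. With that value unrounded and 0.0275 retained, no reading that keeps the stated 7.5% reaches 80% power: it is about 78% one-sided, a small shortfall, and about 68% two-sided, mostly because of sidedness.

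This rests on three assumptions: the bracketed interval in Preliminary Data, which carries no confidence level, is a 95% interval; the two cohorts are independent; and the normal approximation is adequate. The documents do not support a claim that the reported results of the completed study are wrong, or that 0.01 was knowingly substituted. The unstated sidedness and the disagreement between 0.0275 and the printed older-cohort interval affect the power more than this input does.

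**What to change.** In the Sample Size Calculation:

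1. State which younger data form the comparator, and give their AUROC and standard error to at least three decimals with the source interval. For both sequences pooled this is 0.957 and 0.0143; for the quiet arm, supply its own standard error.
2. Settle the older-cohort standard error: either 0.0275, with the interval corrected to 0.82 to 0.93, or about 0.031, which matches 0.81 to 0.93.
3. Name the sidedness, carry both inputs unrounded, and restate the power and detectable difference. With 0.0275 and 0.0143, 80% power is for a difference of about 0.087 two-sided or 0.077 one-sided.

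If 0.01 came from another calculation, say which. The cost is a few restated figures that become somewhat less favourable. No subjects, data or analyses are added.

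### The stated 80% power for a 0.075 AUROC difference holds only for an undeclared one-sided test, and the printed standard error and 95% interval disagree

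*Combined protocol and SAP*

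**What the plan says.** All the figures are in one paragraph under SAMPLE SIZE CALCULATION.

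- Younger adults, earlier study: AUROC 0.95 in quiet runs and 0.97 in interactive runs, and "the standard error of the summary AUROC was 0.01".
- Older adults: "If the discrimination is substantially lower in older adults, we would expect an AUROC of 0.875". Twenty participants "would produce a 95% confidence interval of width 0.12 (0.81 to 0.93) and a standard error of 0.0275".
- Comparison: the standard error of the difference "would be 0.03 and would provide 80% power to detect a difference in AUROCs of 7.5% at the 0.05 significance level".

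The comparison itself is planned under DATA ANALYSIS: "This ROC curve will be compared to that of subjects in the 20-39 year-old range". Neither section says whether the test is one-sided or two-sided.

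**The concern.** A reader will take a test of a difference at the 0.05 level, set beside 95% intervals, as two-sided. On that reading the printed inputs do not give 80%. In addition, the standard error and the confidence interval for the older-adult AUROC stand in the same sentence, describe the same quantity, and do not correspond.

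This is the only power statement in the document, and it supports the comparison of the older ROC curve with the younger one. At the printed standard errors, a two-sided test would miss a true 0.075 drop 27 to 30% of the time, not 20%. A non-significant result could then be over-read as showing that the younger-adult scale carries over, which is a question the AIMS section sets out to answer. The mismatch between standard error and interval affects the stated precision of the older-adult AUROC, which the sample size section ties to the primary objective. The interval likelihood ratios have their own precision statement and are not affected.

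**Working it through.** **Inputs, all from SAMPLE SIZE CALCULATION:** difference 0.075 (which equals 0.95 − 0.875), SE of the difference 0.03, component SEs 0.0275 (older) and 0.01 (younger), level 0.05.

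**Power.** Formula: power = Φ(difference/SE − z), with z = 1.960 two-sided and 1.645 one-sided.

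1. The plan's 80%, reproduced: one-sided, Φ(0.075/0.03 − 1.645) = Φ(0.855) = 80.4%.
2. Two-sided, same inputs: Φ(2.5 − 1.960) = Φ(0.540) = 70.5%.
3. From the component SEs: √(0.0275² + 0.01²) = 0.0293, which rounds to the printed 0.03. Two-sided power is 72.7% and one-sided 82.1%.
4. SE needed for two-sided 80%: 0.075/(1.960 + 0.842) = 0.0268.
5. Difference detectable with two-sided 80%: 2.802 × 0.03 = 0.084, or 2.802 × 0.0293 = 0.082.

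**Can rounding explain it?** No. The SE of the difference cannot fall below the older-group SE, and even with a younger-group SE of zero the two-sided power is Φ(0.075/0.0275 − 1.960) = 77.9%. Taking the difference as 0.0755 gives 71.1% at SE 0.03.

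**SE against interval.**

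| Method | 95% limits | Width |
|---|---|---|
| Printed | 0.81 to 0.93 | 0.12 |
| 0.875 ± 1.96 × 0.0275 | 0.821 to 0.929 | 0.108 |
| t with 19 df, SE 0.0275 | 0.817 to 0.933 | 0.115 |
| Logit scale, SE 0.0275 | 0.810 to 0.920 | 0.109 |

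No version gives both printed limits. The t interval comes closest: its width and upper limit round to the printed values, but its lower limit rounds to 0.82. Working back, the printed width implies SE = 0.12/3.92 = 0.0306. For an interval symmetric about 0.875, a lower limit that rounds to 0.81 needs a half-width of at least 0.060, and an upper limit that rounds to 0.93 needs one of at most 0.060. So about 0.0306 is the only normal-theory SE that fits both limits.

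**Hanley-McNeil check** (the method the plan cites). Assumptions: independent readings, high-exposure readings as the positive group, and the earlier study's time points (4 high, 2 low per run). With A = 0.875, Q1 = A/(2 − A) = 0.7778, Q2 = 2A²/(1 + A) = 0.8167, A² = 0.7656:

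SE² = [A(1 − A) + (H − 1)(Q1 − A²) + (L − 1)(Q2 − A²)]/(H × L), where H and L are the numbers of high and low readings.

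- One run, 20 subjects (H = 80, L = 40): SE 0.0309, interval 0.814 to 0.936, width 0.121. This matches the printed width but not the printed upper limit.
- Two runs, 20 subjects (H = 160, L = 80): SE 0.0218, width 0.085. This matches neither printed figure.

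**Conditional power for 0.075, younger SE 0.01:**

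- Older SE 0.0306: SE of the difference √(0.0306² + 0.01²) = 0.0322, giving 64% two-sided and 75% one-sided.
- Older SE 0.0218: SE of the difference √(0.0218² + 0.01²) = 0.0240, giving about 88% two-sided.

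**The case against.** The strongest reply is that the 80% is not a miscalculation. It follows from the printed inputs as a one-sided test, and the scenario is directional, since only a lower AUROC in older adults is contemplated. That stands as far as it goes: what is established is an unstated sidedness, and 70.5 to 72.7% is the consequence of the conventional reading. But the power sentence refers to a difference without direction, and a one-sided test has to be declared for the reader to rely on it.

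A second reply is that the 80% may come from another comparator. PRELIMINARY DATA gives "AUROC = 0.957 [0.929 to 0.985] in all runs" and allows the younger data to come from the quiet arm "or from both infusion sequences as appropriate". Then 0.957 − 0.875 = 0.082, and two-sided power at SE 0.0293 is 80.0%. This is possible but conjectural, and on this account the printed 7.5% would be the wrong figure. It also keeps the younger SE at 0.01, whereas the quoted interval implies (0.985 − 0.929)/3.92 = 0.0143, at which power for 0.082 is about 75%.

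Third, the interval discrepancy is small, about 0.01 in one limit if a t interval was used. That is fair as to size, but the plan does not say that a t interval was used.

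Finally, a reader might infer that the study as run has less than 80% power. The document does not support that. The Design section describes one 35-minute sequence, while DATA ANALYSIS describes paired conditions. Two runs per subject would, on independent readings, give more than 80%.

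**Conclusion.** The point holds as an inconsistency in the planning paragraph. At the printed difference and standard errors, two-sided power is 70.5 to 72.7% rather than 80%, and the stated figure is recovered only by a one-sided 0.05 test that is nowhere declared. The printed SE of 0.0275 and the printed interval of width 0.12 cannot both be right under a normal, t or logit interval, and the document does not show which is the slip. If about 0.031 is right, power for 0.075 is about 64% two-sided and 75% one-sided. If each subject contributes two runs, it is about 88% two-sided.

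Two stronger conclusions are not supported: that a one-sided test was intended, and that the design as run is underpowered. The power figures use a normal approximation. The Hanley-McNeil figures also assume independent readings, although readings are repeated within subjects and the document gives no within-subject correlation. The correction is worth making, but the sample size does not turn on it.

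**What to change.** Keep 20 participants and revise the one paragraph:

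1. State the number of runs, and of high and low readings, per older subject. Reconcile the single sequence in the Design and Study Protocol sections with the paired conditions in DATA ANALYSIS.
2. Recompute the SE and the 95% interval from those counts so that they agree, name the interval method, and say whether readings are treated as independent.
3. Name the younger-adult run or runs to be compared, and take the AUROC and its SE from the same source.
4. Then either restate two-sided power for 0.075 (about 70 to 73% at the printed SEs, equivalently an 80%-power detectable difference of 0.082 to 0.084), or declare and justify a one-sided 0.05 test.

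The cost is wording only. The downside is that the stated power may become less favourable. If a one-sided test is chosen instead, the study could not show better discrimination in older adults.
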